## 6.18 Serious Adverse Events

A serious adverse event (SAE) is defined as any adverse drug experience occurring at any dose that results in any of the following outcomes:

- Death;
- Life threatening situation (subject is at immediate risk of death);
- Inpatient hospitalization or prolongation of existing hospitalization (excluding those for study therapy or placement of an indwelling catheter, unless associated with other serious events);
- Persistent or significant disability/incapacity;
- Congenital anomaly/birth defect in the offspring of a subject who received study treatment;
- Other: Important medical events that may not result in death, be immediately life threatening, or require hospitalization, may be considered a SAE when, based upon appropriate medical judgment, they may jeopardize the subject and may require medical or surgical intervention to prevent one of the outcomes listed in this definition. Examples of such events are: Intensive treatment in an emergency room or at home for allergic bronchospasm; Blood dyscrasias or convulsions that do not result in hospitalization; Development of drug dependency or drug abuse.

### 6.18.1 Serious Adverse Event Reporting Requirements

Any clinical adverse event or clinically significant abnormal laboratory test value that is serious and which occurs during the course of the study, regardless of the treatment arm, occurring from the time the subject signs the Informed Consent (start of study screening procedures), must be reported to Noven within one working day of the investigator becoming aware of the event.

Amendment 4: Version 5.0 May-08-2013

Amendment 3: Version 4.0 December-11-2012

Amendment 2: Version 3.0 October-31-2012

Amendment 1: Version 2.0 August-02-2012

Final Protocol May-25-2012

Serious Adverse Events with a start date within 30 days of last patch removal MUST be collected and reported.

Suspected Unexpected Serious Adverse Reactions are reported to investigators at each site and associated IRB/IEC when the following conditions occur:

- The event must be a SAE.
- There must be a certain degree of probability that the event is an adverse reaction from the administered drug.
- The adverse reaction must be unexpected, that is to say, not foreseen in the Investigator's Brochure.

When all subjects at a particular site are off treatment as defined by the protocol:

- only individual reports originating in that particular trial will be forwarded to the site and associated IRB/IEC on an expedited basis;
- individual reports considered to be a significant safety issue and/or which result in Sponsor recommending a change to the Informed Consent Form (ICF), will be reported in an expedited manner to all investigators and IRBs/IECs;
- individual reports originating from other trials using the same investigational product will be provided as six monthly reports to investigators and IRBs/IECs where long-term follow-up studies are carried out, unless they are considered significant.

A female subject must be instructed to stop taking the study drug and immediately inform the investigator if she becomes pregnant during the study. The investigator should report all pregnancies to Noven within one working day of the investigator becoming aware of the event. The investigator should counsel the subject and discuss the risks of continuing with the pregnancy and the possible effects on the fetus. Monitoring of the patient should continue until conclusion of the pregnancy. Pregnancies occurring up to 30 days after the completion of the test "drug" must also be reported to the investigator. Pregnancy occurring in the partner of a male subject participating in the study should be reported to the investigator and the sponsor. The partner should be counseled, the risks of continuing the pregnancy discussed, as well as the possible effects on the fetus. Monitoring of the patient should continue until conclusion of the

Amendment 4: Version 5.0 May-08-2013

Amendment 3: Version 4.0 December-11-2012

Amendment 2: Version 3.0 October-31-2012

Amendment 1: Version 2.0 August-02-2012

Final Protocol May-25-2012

pregnancy and follow-up pregnancy reports must be submitted to sponsor within 24 hours. If subject is lost to follow-up then this should be documented in a follow-up report.

This study adheres to the definition and reporting requirements of "ICH Guideline for Clinical Safety Data Management, Definitions and Standards for Expedited Reporting, Topic E2."

### **6.19 Anticipated Adverse Events**

Some of the adverse events noted in more than one clinical trial of oral forms of d/l-amphetamine are: headache, decreased appetite, stomach ache, trouble sleeping, nervousness, mood swings, weight loss, dizziness, dry mouth, blurred vision, seizures (mainly in patients with a history of seizures), and slowing of growth in children. It should be assumed that the adverse event profile for the d-ATS should be similar to that found in clinical trials of oral d/l-amphetamine.

## **7 STUDY TREATMENT**

### **7.1 Investigation Product and Reference Treatment**

#### **7.1.1 *Investigational Product***

d-ATS contains [REDACTED]. Each patch is designed to release d-amphetamine upon application to intact skin and contains about [REDACTED]  
[REDACTED]

Each d-ATS patch comprises 3 layers. Proceeding from the visible surface toward the surface attached to the skin, these layers are: (1) A translucent flexible film; (2) an adhesive formulation containing amphetamine; and (3) a release liner, which is attached to the adhesive surface and must be removed before the patch can be used. The investigational product will be supplied by Noven. Table 6 identifies the drug product and dosage formulations to be used in this study.

**Table 6.**

d-Amphetamine Transdermal Drug Delivery System(d-ATS)	5 mg/4.76 cm  9-hour patch
d-Amphetamine Transdermal Drug Delivery System(d-ATS)	10 mg/9.52 cm  9-hour patch
d-Amphetamine Transdermal Drug Delivery System(d-ATS)	15 mg/14.29 cm  9-hour patch
d-Amphetamine Transdermal Drug Delivery System (d-ATS)	20 mg/19.05 cm  9-hour patch

Amendment 4: Version 5.0 May-08-2013  
Amendment 3: Version 4.0 December-11-2012  
Amendment 2: Version 3.0 October-31-2012  
Amendment 1: Version 2.0 August-02-2012  
Final Protocol May-25-2012

### 7.1.2 *Reference Treatment*

The reference treatment for use during this study is a placebo patch which will be identical in appearance to d-ATS. The placebo patches will be supplied by Noven.

## 7.2 Dosage and Administration

**Dose-Optimization Period:** During the five week dose optimization period subjects will receive d-ATS. Subjects will be instructed to apply one patch daily for 9-hours. Patch will be removed after 9-hours and a new patch will be applied the next day.

Dosing on Visit 1 will begin with the lowest strength of d-ATS. Based upon the ADHD-RS-IV score, CGI-I score and tolerability, subjects will receive the next available dose of d-ATS until optimal dose is achieved.

**Double-Blind Treatment Period:** Administration of double blind study medication will begin on Day 36 and continue up to Day 49. Subjects/parents/caregiver will be instructed to apply patch once daily in the morning and remove the patch after 9 hours. A new patch will be applied the next day. Subjects must continue to apply the patches up to the day of their clinic visit. Day 42 and Day 49 patches will be applied in the clinic by subject/parent/caregiver/site personnel.

## 7.3 Randomization and Blinding

Randomization will occur prior to the start of the double-blind study period. Subjects will be randomized to one of the two treatments in a 1:1 ratio. Each eligible subject will be randomized to group assignment by a centralized Interactive Voice Response System (IVRS)/Interactive Web Response System (IWRS). Randomization will be applied centrally across all sites to ensure even distribution of subjects across each treatment sequence.

For the dose-optimization period, the study staff at the clinical site will dispense open-label study drug to all eligible subjects.

For the double-blind treatment period, the study staff at the clinical site will dispense the double blind study medication according to the randomization code as assigned by the IVRS/IWRS. All personnel, including the investigator, site personnel, sponsor or designee, and the study subject

Amendment 4: Version 5.0 May-08-2013

Amendment 3: Version 4.0 December-11-2012

Amendment 2: Version 3.0 October-31-2012

Amendment 1: Version 2.0 August-02-2012

Final Protocol May-25-2012

will be blinded to the medication codes. The medication codes will not be available to the study personnel until completion of the study and final data review (clinical database lock) except in the case of an emergency.

In the case of an emergency, if the investigator deems identification of the study drug necessary for the purpose of providing urgent patient care, and knowledge of the subject's treatment assignment will alter subsequent care, then the investigator is authorized to break the blind at the clinical site. Whenever possible, the medical monitor must be notified prior to unblinding. In the event that this is not possible, the medical monitor must be notified within 24 hours of unblinding.

## **7.4 Prior and Concomitant Therapy**

### ***7.4.1 Rules for Recording Prior and Concomitant Therapies***

Concomitant therapy is defined to include all medications, procedures, and therapies that are used to treat the subject during the study. Rules for recording therapies are as follows:

- In the case of an AE, all concomitant therapies used to treat the AE will be recorded.
- All concomitant medications and over-the-counter medications that are ongoing as of the date of the informed consent and taken during the study must be documented.

### ***7.4.2 Ongoing, Prior and Concomitant Therapies***

Rules for ongoing prior and concomitant therapies are as follows:

- Prescription medication for stable medical, non-psychiatric illness will be permitted during the study provided the dose has remained stable for 30 days prior to screening.
- Use of an investigational study medication within 30 days prior to screening is not permitted

### ***7.4.3 Prohibited Concomitant Medication***

Subjects will not be allowed to take the following medications and therapies during the entire duration of the study:

- Any stimulant other than study drug (e.g. methylphenidate, amphetamine, Ritalin, Ritalin SR, Metadate ER, Concerta, dextromethylphenidate, Focalin, dextroamphetamine, Dexedrine, Adderall)
- Atomoxetine (Strattera), SSRIs and SNRIs

Amendment 4: Version 5.0 May-08-2013

Amendment 3: Version 4.0 December-11-2012

Amendment 2: Version 3.0 October-31-2012

Amendment 1: Version 2.0 August-02-2012

Final Protocol May-25-2012

- Tricyclic antidepressants
- Clonidine, MAOIs
- Mood Stabilizers (e.g. lithium, valproate, quetiapine)
- Antipsychotics (e.g. risperidone, olanzapine)
- Anticonvulsants
- Sedative hypnotics (unless stable dose at least 30 days prior to screening and during the clinical study)
- Coumarin anticoagulants
- Halogenated anesthetics
- Phenylbutazone
- Alternative therapies to treat ADHD
- Other investigational drugs

## 7.5 Treatment Compliance

Subjects/parents/caregivers will be instructed to bring used and unused patches to their clinic visits. Site personnel will collect all used and unused patches at each clinic visit and perform drug accountability and clarify any discrepancies with the subject/parent/caregiver during the clinic visit.

## 7.6 Investigation Product and Reference Treatment Management

### 7.6.1 *Packaging and Labeling*

Packaging and labeling will be performed by Noven or designee in conformance with all regulatory requirements.

### 7.6.2 *Drug Accountability*

The d-Amphetamine transdermal patch is a Schedule II controlled substance (CII) and the Investigator and/or designee must follow federal, state and local regulations governing the handling and distribution of CII substances. Upon receipt of the study medication, the Investigator, site pharmacist, or study coordinator will inspect and inventory the medication. Under no circumstances will the Investigator allow the study drug to be used other than as

Amendment 4: Version 5.0 May-08-2013

Amendment 3: Version 4.0 December-11-2012

Amendment 2: Version 3.0 October-31-2012

Amendment 1: Version 2.0 August-02-2012

Final Protocol May-25-2012

directed by the protocol.

Study treatments will be stored in a room that is monitored for temperature. Study drug should be stored pouched below 77°F (25°C). All study treatments will be kept in a dry, locked, and secured storage facility accessible only to those authorized by the Investigator to dispense the study medication. All storage conditions required for storage of CII substances will be followed. An accurate and timely record of the receipt of all clinical supplies and subsequent return of drug to the Sponsor must be maintained. This includes, but may not be limited to: (a) documentation of receipt of clinical supplies, (b) study drug dispensing/return reconciliation log, (c) study drug accountability log, and (d) all shipping service receipts. All forms will be provided by the Sponsor. Any comparable forms that the investigational site wishes to use must be approved by the Sponsor.

Used and unused patches will be retained at the site until the Sponsor requests their return or destruction.

## **8 STATISTICAL METHODS**

The Sponsor or designee will perform data analysis.

### **8.1 Determination of Sample Size**

Assuming a standard deviation (SD) of [REDACTED] and based on an average difference in total SKAMP scores between Placebo and d-ATS of [REDACTED] [REDACTED], 74 subjects would need to complete the study to detect a true difference of [REDACTED] in mean total SKAMP scores between placebo and d-ATS at 80% power when testing at a significance level of  $\alpha = 0.05$  (2-sided). Assuming a dropout rate of 20%, 90 subjects will be randomized and it is expected that 74 subjects will complete the study. .

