**CONFIDENTIAL**

	
attempted suicide, has recent (last 6 months) suicidal ideation or any lifetime self harm event;
 

• Has a history of abnormal thyroid function;

• Has BMI for age greater than 95th percentile per CDC BMI-for-gender specific charts;

• Has a known history of symptomatic cardiovascular disease, advance arteriosclerosis, structural cardiac abnormality, cardiomyopathy, serious heart rhythm abnormalities, coronary artery disease, or other serious cardiac problems that may place them at increased vulnerability to the sympathomimetic effects of a stimulant drug;

• Has any skin abnormality present at the potential application site that is likely to be aggravated by the study drug (i.e., infection, rash, atrophy, excessive fragility or dryness, any cut or abrasion, or tattoo);

• Has a history of hypersensitivity, allergy to topical medication, preparation, or adhesive dressings;

• Has concurrent chronic or significant acute illnesses (such as severe allergic rhinitis or an infectious process requiring antibiotics, unless expected to resolve or has resolved by Day 0) disability or any unstable medical condition that in the investigator's opinion would lead to difficulty complying with the protocol requirements;

• Has used any investigational drug within 30 days of the screening visit;

• Has a history of physical, sexual, or emotional abuse in the last year;

• Has a medical history of Hepatitis A, B,C or HIV;

• Has positive urine drug screen for drugs of abuse.

Planned Sample Size:	Sufficient number of subjects will be screened such that at least 90 subjects (6 to 17 years of age) are randomized into the study and at least 74 subjects complete the study. Completers will be defined as subjects who have received both treatments during the double-blind treatment period and have completed both 12-hour classroom sessions during the double-blind treatment period.

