**Double-Blind Treatment Period [Day 36 to Day 49; Visit 6 (Day 42) and Visit 7 (Day 49)]:**

Subjects who have reached an optimal dose will be randomized at Visit 5 to receive double-blind treatment. Administration of study medication will begin on Day 36 and continue up to Day 49 (end of Week 7). During Week 6 subjects will receive study patches in accordance with the randomization schedule and during Week 7 subjects will cross-over to receive the other study treatment per the randomization schedule. Subjects/parents/caregivers will be instructed to apply study patches to the hip once daily in the morning at approximately 8:00 am. Patches will be removed after 9 hours. Each day a new patch will be applied to the opposite hip. Subjects will be instructed to continue completing the daily dosing diary and the daily dermal diary. Subjects will return to the clinic for evaluations and analog classroom sessions in the laboratory classroom setting on Visit 6 (Day 42) and Visit 7 (Day 49). Site personnel will contact subjects by telephone on Day 39 and Day 46. All end of study procedures will be completed for subjects who are early discontinuations from the study.

**Follow-Up:** A safety follow-up by telephone 7- 10 days (Visit 8, Day 56 + 3 days) after last dose of study drug.

**Sample Size:** Sufficient number of subjects with ADHD will be screened to randomize approximately 90 subjects. Assuming a 20% dropout rate, it is expected that 74 subjects will complete the study. The Full Analysis Set population (FAS) will be used as the primary population for analysis of efficacy endpoints and is defined as subjects who have taken at least one dose of study medication.

Amendment 4: Version 5.0 May-08-2013

Amendment 3: Version 4.0 December-11-2012

Amendment 2: Version 3.0 October-31-2012

Amendment 1: Version 2.0 August-02-2012

Final Protocol May-25-2012

**Study Duration:** The duration of the study will be approximately 56 days for each individual subject (not including screening and washout).

**Study Population:** The study population will consist of children and adolescents 6 to 17 of age, who have been diagnosed with ADHD.

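### The sample-size figures do not agree: 20% dropout from 90 randomised leaves 72 completers, not the 74 on which the 80% power is based

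*Protocol*

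**What the plan says.** Protocol 8.1 (Determination of Sample Size) makes two linked statements. The first fixes the number that must finish: "74 subjects would need to complete the study to detect a true difference of" a redacted amount, "at 80% power when testing at a significance level of" 0.05, two-sided. The second says how that number will be reached: "Assuming a dropout rate of 20%, 90 subjects will be randomized and it is expected that 74 subjects will complete the study".

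The same figures appear in three other places:

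- Protocol synopsis, Sample Size Calculations: the same 20%, 90 and 74.
- Protocol 5.1, Sample Size paragraph: enough subjects will be "screened to randomize approximately 90 subjects", and "Assuming a 20% dropout rate, it is expected that 74 subjects will complete the study".
- SAP 3.1 (Sample Size Considerations): the same sentence as Protocol 8.1. SAP 1.1 reports no changes from protocol amendment 4.

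A fifth place, the synopsis entry on planned sample size, gives no dropout rate but sets minimum targets: "at least 90 subjects (6 to 17 years of age) are randomized into the study and at least 74 subjects complete the study". The synopsis and SAP 3.1 define a completer as someone who received both double-blind treatments and finished both 12-hour classroom sessions.

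**The concern.** The dropout sentence is there to show that randomising 90 is enough to end with 74. It gives three exact figures, any two of which determine the third, and the third is not the one printed. The redactions do not affect this check, since the dropout rate, the randomised number and the completer number are all visible.

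At stake is whether a reader can rely on the stated basis for the power. Anyone who takes the 20% and the 90 at face value will expect two fewer completers than the plan says it needs. Under that assumption, 74 is a number the trial would more often miss than reach.

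**Working it through.** **Inputs.** Dropout 20%, randomised 90, expected and required completers 74, power 80%, two-sided alpha 0.05: all from Protocol 8.1, repeated in SAP 3.1. The standard deviation and the difference are redacted, so the 74 itself cannot be re-derived.

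**Step 1: the plan's own figure.** Completers = randomised × (1 − dropout) = 90 × 0.80 = 72. The plan says 74. The gap is 2.

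**Step 2: solve for each figure in turn.**

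| Held fixed | Solved for | Result |
|---|---|---|
| 90 randomised, 20% dropout | completers | 90 × 0.80 = 72 |
| 74 completers, 20% dropout | randomised | 74 / 0.80 = 92.5, so 93 |
| 90 randomised, 74 completers | dropout | (90 − 74) / 90 = 16/90 = 17.8% |

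**Step 3: what two completers are worth in power.** The standardised paired effect δ is back-solved so that 74 completers give exactly 80%.

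- Normal approximation: δ = (1.960 + 0.842) / √74 = 0.326. Power at 72 = Φ(δ√72 − 1.960) = Φ(0.804) = 78.9%.
- Noncentral t, n − 1 degrees of freedom: δ = 0.330. Power is 80.0% at 74 and 78.9% at 72. With n − 2 degrees of freedom the result is again 78.9%.
- Allowance for rounding: 74 may have been rounded up from just over 73. With δ set so that 73 give 80% (n − 2 degrees of freedom), power is 80.5% at 74 and 79.4% at 72.

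Power at 72 is therefore 78.9% to 79.4%, which is 0.6 to 1.1 points below 80%.

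**Step 4: chance of reaching 74 at a literal 20%.** If dropouts are independent (an assumption made here, not in the plan), the number completing is binomial with n = 90 and probability 0.80. The chance of 74 or more is 35%.

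**Step 5: check of the corrected rate.** 90 × 0.82 = 73.8, which rounds to 74. A rate of about 18% therefore fits 90 and 74. The exact figure is 17.8%.

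**The case against.** A reader might infer from the mismatch that the stated 80% power is not delivered. The documents do not support that, for three reasons.

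- The 80% is attached to 74 completers, not to 90 randomised with 20% lost. If 74 complete, the power statement stands and only the dropout percentage is wrong.
- The synopsis makes both 90 and 74 minimum targets, and Protocol 5.1 and SAP 3 speak of approximately 90. Nothing caps randomisation at 90.
- The primary efficacy population is the full analysis set, analysed with a likelihood-based repeated-measures model (Protocol 8.1.1 and 8.2.1, SAP 6.1 and 7.1.1). A randomised subject who does not complete can still contribute observed scores, so a count of completers may understate the information available.

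All of this stands against the stronger reading, but none of it repairs the sentence. Minimum targets do not make 74 the expected number at 20% loss, and the documents give no replacement rule for making up a shortfall. The contribution of non-completers is also limited. Post-randomisation SKAMP scores come only from Visits 6 and 7, so a subject lost before Visit 6 adds none, and Protocol 8.2 does not allow one classroom day to fill in the other. The plan also chose to express its power in completers.

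It can fairly be said that a dropout rate is a planning guess and that 17.8% is close to 20%. That is a good reason to treat the point as small. But the text does not present 20% as a rounded figure, and rounding to whole subjects does not turn 72 into 74.

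A reader might also guess that the 74 was multiplied by 1.2 instead of divided by 0.8. That gives 88.8, or 89, not 90, and the documents do not say how 90 was chosen. The cause is best left open.

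**Conclusion.** The sample-size statement is internally inconsistent in four places: the synopsis calculation, Protocol 5.1, Protocol 8.1 and SAP 3.1. At 20% dropout, 90 randomised yield two completers fewer than the plan states and requires. This part is plain arithmetic and rests on no assumption.

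The consequence is minor: at a literal 20% loss, completer-based power falls by about one point. That size depends on a paired comparison and on 74 completers giving 80%. The visible text does not name the test behind the 74, and the redactions, which are not a fault in the plan, prevent a direct calculation. The finding is an incorrect planning figure to be restated. It does not show that the trial is underpowered.

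**What to change.** Make the figures agree in the synopsis (Sample Size Calculations), Protocol 5.1, Protocol 8.1 and SAP 3.1, in one of two ways:

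1. **Preferred.** Change the dropout assumption to about 18% (16 of 90), keeping 90 randomised, 74 completers and 80% power. This agrees with the minimum targets in the synopsis entry on planned sample size, which then needs no change.
2. **If 20% is the intended assumption.** State 72 expected completers and about 79% power, and reconcile the synopsis target of at least 74 completers and the statement that 74 need to complete. Without that, this option creates a new contradiction.

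The first option costs one sentence in each of the four places. The second also requires edits to the synopsis target and to the power sentence. Neither needs extra enrolment or a change to the analysis. The price is a slightly smaller dropout margin in the first case, or a slightly lower stated power in the second.
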